STUDY ID: NCT02779491.

EVALUATION OF A 5-A-DAY FRUIT AND VEGETABLE MOBILE PHONE APPLICATION

STUDY PROTOCOL AND STATISTICAL ANALYSIS PLAN

DOCUMENT DATE: 15.04.19

METHODS

Evaluation of the app was undertaken using a randomized controlled pilot trial, where volunteers were randomized to receive or not receive the app for either two weeks or four weeks and FV knowledge, FV intake and FV behaviour were assessed and compared at baseline and at study end.

Volunteers

Volunteers to test the app were recruited from the staff and students of Bournemouth University, UK, from Nov., 2015 to March, 2017. We aimed to recruit 100 volunteers - 50 to test the app and 50 to act as controls. No earlier research was available to allow power calculations, thus 50 volunteers were considered sufficient to gain feedback and assess potential impacts of the app, while remaining manageable should few impacts be found. Adult volunteers (aged 18 years and over) were required to own an Android smart phone, as the app was only developed for Android platforms, but there were no other inclusion / exclusion criteria to maximise the generalisability of the study. Volunteers were recruited for a study to 'test a novel mobile phone app for encouraging healthy behaviours'. Volunteers were thus aware at the study start, that they may or may not receive an app to test, but they were informed that that the app may target one of a number of health behaviours, such as exercising, stress reduction or healthy eating.

Intervention / Control

Volunteers were randomized to receive the app (intervention) or not receive the app (control). Randomization was undertaken on study entry by drawing lots, and recruitment stopped once 50 individuals had been randomized to test the app. All volunteers who received the app were asked to download the app onto their phones, to register with the app to set-up a user profile, and to use the app as often as they wished for either a two week or a four week period. The app was tested for two weeks from Nov. 2015 - March 2016 and from Nov. 2016 - March 2017, and for four weeks from June 2016 - August 2016.

Outcomes

Awareness of the 5-a-day FV recommendations, FV knowledge and FV intake were assessed as outcomes, at baseline, at a mid point, and at study end. Awareness of the recommendations, FV knowledge and self-reported FV intakes were assessed using a questionnaire previously developed by ourselves [1]. The questionnaire consisted of two questions on awareness of the 5-a-day message, four questions on knowledge of the details of the message (which foods are included, portion sizes, the need for variety, reasons for consumption), and two questions on FV intake, as

detailed below. FV behaviour was also assessed as part of the trial using a behavioural measure. Two questions on demographic and lifestyle characteristics that have previously been associated with FV consumption and dietary knowledge [1-9] were also assessed as potential confounders. All volunteers (intervention and control) completed all outcome assessments in the same manner.

Awareness of the recommendations: Awareness of the recommendations were assessed using two open-response questions: 'Are you aware of the 5-a-day FV message?' and 'What do you think it means?'

FV knowledge: FV knowledge was assessed using four structured closed-response questions on: 1) the FV that are included in the message; 2) the portion sizes that are required for the message; 3) the variety that is required for the message; and 4) the reasons for FV consumption. These questions include 1) a number of foods; 2) a number of different portions of FV; 3) a number of combinations of FV to be consumed in a day; and 4) a number of different health conditions, respectively, and respondents were asked to report 1) inclusion in the recommendations or not; 2) contribution to the recommendations based on portion sizes; 3) number of FV portions consumed in the day; and 4) impact of FV on each health condition, respectively. For all questions, a correct response, based on current recommendations from the UK Government [10], was scored +1, an incorrect response was scored -1, and 'don't know / not sure' was scored 0. Missing values were also completed with 0, where found.

Self-report FV intake: FV intake was assessed using one open-response structured question requesting household amounts (e.g. tablespoons) of all FV consumed at various time points (before breakfast, breakfast, morning, lunch, afternoon, evening meal, evening) on a typical weekday and on a typical weekend day, and one open-response question asking for estimated number of portions of FV consumed per day. The structured question was used to calculate portions of FV consumed per day (calculated FV), while the single question was used to provide an estimated measure (estimated FV).

FV Behaviour: FV intake was also assessed using a behavioural measure. Volunteers were offered a drink while completing all questionnaires, and given the choice of a tea, coffee, water or fruit smoothie. Selections of the fruit smoothie were considered an FV choice, while all other drinks were considered a non-FV choice. No drink was also a permitted option.

Demographic and Lifestyle Characteristics: Demographic and lifestyle characteristics also assessed were: gender, age, marital status, living status, number of years of education, smoking habits, alcoholic drinking habits, dietary supplement taking habits, and height and weight (to calculate BMI).

App Feedback

Number of uses were requested from volunteers who received the app, and downloaded from the app itself. Volunteers who received the app were also asked to feedback on their experiences and offer suggestions for the app.

Psychological Stress

To encourage a perception that healthy eating was not necessarily the focus of the study, the Psychological Stress Measure [11] was also provided to participants. This questionnaire consists of 49 statements relating to somatic, cognitive-affective and behavioural outcomes of stress.

Respondents rate the extent to which they have experienced these outcomes in the last week on an 8-point scale ranging from 1 (not at all) to 8 (extremely). These data were not analysed.

Procedure

Volunteers undertook all outcome assessments at the Eating Behaviours Laboratory, Bournemouth University, UK. On each assessment occasion, volunteers completed all questionnaires, were offered a drink, and had every opportunity to ask questions. One researcher randomized all volunteers and dealt with all queries ([name]), while another researcher oversaw all outcome assessments, thus this researcher was blind to treatment ([name]).

The study was given ethical approval by the Research Ethics Committee of Bournemouth University, prior to commencement, and was registered as a clinical trial on www.clinicaltrials.gov (ID NCT02779491). Methods were undertaken as detailed in the trial registration with the exception that a behavioural measure of FV intake was added to the study prior to commencement, and a measure of FV attitudes was not undertaken. Attitudes towards FV were not measured to reduce demand characteristics given the extensive FV knowledge questionnaire. All participants provided written informed prior to starting the study.

Analysis: Data were analysed on an Intention-to-Treat basis, where missing data were completed using Last Observation Carried Forward. Demographic and lifestyle variables and all measures at baseline were first described and compared using t-tests, based on study duration and app / control

grouping. Several important differences were found between those studied for two weeks and those studied for four weeks, thus study duration was included in all subsequent analyses. All FV knowledge and intake outcome assessed by questionnaire were analysed using 2 (study duration) x 2 (app / control) x 2 (baseline / study end) mixed ANOVA. Our behavioural measure of FV intake – choice of fruit drink or non-fruit drink was analysed using Chi-squared tests. All data are reported as means and standard deviations. Significance was set at p<0.05.

REFERENCES

- 4. Ashfield-Watt PAL. Fruit and vegetables, 5+ a day: are we getting the message across? Asia Pac J Clin Nutr. 2006;15:245-52.

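### Does fixing app duration by calendar period, not by lot, undermine the 2x2x2 ANOVA?

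*Combined protocol and SAP*

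**What the plan says.** The Methods introduction summarises the design loosely: "volunteers were randomized to receive or not receive the app for either two weeks or four weeks". The Intervention / Control section is more exact. It describes one allocation, app or no app, and the mechanism: "Randomization was undertaken on study entry by drawing lots". No allocation step for duration is described. The same section dates the testing. Four-week testing has a single period: "and for four weeks from June 2016 - August 2016". Two-week testing has a winter on either side of it: "The app was tested for two weeks from Nov. 2015 - March 2016 and from Nov. 2016 - March 2017".

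The Analysis paragraph reports the baseline comparison by duration and by group: "Several important differences were found between those studied for two weeks and those studied for four weeks". It gives this as the reason for carrying study duration into all later analyses. Questionnaire outcomes on knowledge and intake go into a "2 (study duration) x 2 (app / control) x 2 (baseline / study end) mixed ANOVA", and "Significance was set at p<0.05". The documents give no number of volunteers per duration group, no SD and no hypothesis about duration.

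**The concern.** The two-week and four-week periods share no calendar month, and there was only one four-week period. Duration is thus the same variable as membership of the summer 2016 block. Adjustment cannot pull the two apart, and the baseline differences, seen before anyone had used the app, show that the blocks differed in more than length of use.

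The label invites a causal reading all the same. The factor is called study duration, four of the seven ANOVA terms contain it, none is exempt from the significance threshold, and the introductory sentence can be read as if duration had been randomised. If duration x app x time were significant, a reader might conclude that longer use changes the app's effect. The design cannot support that conclusion, and the plan does not say so.

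**Working it through.** **Inputs from the document.** Planned size 100 (50 app, 50 control); testing periods as dated in Intervention / Control; threshold 0.05, taken as two-sided. The plan has no power calculation, so there is no figure of its own to reproduce.

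**Assumptions.** Change-score SD of 1, near-equal arms in each block, and a split between blocks. Even monthly recruitment over 10 two-week months and 3 four-week months gives 10/13 = 76.9%, so about 77/23. The splits 85/15 and 67/33 show the range.

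**1. Terms.** Duration (D), app (A), time (T), DxA, DxT, AxT, DxAxT: 7 terms, 4 of which contain D.

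**2. Is duration separable from the summer block?** On change scores the three-way term becomes app x duration. A design matrix with intercept, app, duration and app x duration has rank 4 from 4 columns. Adding summer and app x summer gives 6 columns and the rank stays at 4. The two explanations are fully aliased.

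**3. Is it aliased with calendar time in general?** Not entirely. The winters centre on mid-January 2016 and mid-January 2017, which average to mid-July 2016, the centre of June to August 2016. If the two winters recruited about equally (the document does not say), a linear trend over time is roughly balanced across duration. What is fully aliased is whatever was specific to that summer: season and who was recruited then.

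**4. How often could the misreading arise?** The three-way contrast is the app-control difference in change in the four-week block minus that in the two-week block.

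- Standard error at 77/23: sqrt(1/38 + 1/39 + 1/12 + 1/11) = 0.476 SD.
- Smallest significant estimate, on 96 df: 1.985 x 0.476 = 0.944 SD.
- Probability of significance (noncentral t) with no true duration effect, at 77/23: 8.2%, 18.0% and 54.8% when the app effect is 0.25, 0.5 and 1.0 SD larger in summer.
- At 0.5 SD with other splits: 14.3% at 85/15 (SE 0.561, smallest significant estimate 1.114) and 21.4% at 67/33 (SE 0.425, smallest significant estimate 0.845).
- With no difference between blocks, simulation at 77/23 gives 5.0%, the nominal rate.

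These are not false positives. The term correctly detects that the app effect differed between blocks; only attributing this to length of use would be unsupported.

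**5. Is the randomised comparison affected?** No. App and control were drawn by lot for volunteers entering in the same period, so the app-control difference in change is randomised within each block and app x time combines those differences. Its standard error with 50 per arm is sqrt(2/50) = 0.20 SD if the blocks are pooled by size, or 0.476/2 = 0.238 SD at 77/23 if they are weighted equally. Removing the duration factor would only discard a sensible block adjustment.

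**6. Could an added analysis recover a duration effect?** The only candidate is the app-control difference in change from mid point to study end among four-week volunteers. By noncentral t, 80% power needs about 1.57 SD with 15 such volunteers and 1.23 SD with 23, and the document does not say when the mid point falls. Nothing useful would be gained.

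**The case for a change.** The strongest case for a change is that it would cost almost nothing. A sentence saying that duration was set by period, a block name for the factor and a clearer introduction would remove any chance of misreading, at the sole loss of a two-versus-four-week claim that the design never supported. The factorial model produces and tests the three-way term whether or not anyone intended to interpret it, and a caveat could still guide reporting after the trial is over.

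The factual part of this stands: duration was not randomised, no limit on interpretation is written down, and the introductory sentence is ambiguous. What does not follow is that the plan is at fault. The Intervention / Control section settles the ambiguity by describing a single allocation and dating each period. The Analysis paragraph gives baseline differences as its only reason for the factor, which is adjustment. The feared conclusion is a prediction about a reader and appears nowhere in the text. The document is dated 15.04.19, after recruitment closed in March 2017, and describes a pilot in the past tense. A caveat on non-randomised terms belongs beside the results, if such a term is discussed at all.

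**Conclusion.** No change to the plan. Duration terms are block contrasts and cannot isolate length of use; that follows from the dates alone and needs no assumption. The plan makes no use of them that depends on the opposite. It gives the dates and reports the baseline differences, so an analyst has what is needed to read the terms properly. The app x time comparison rests on randomisation, and duration x app x time remains a valid test of whether the app effect differed between blocks.

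The exposure is limited to interpretation. A 0.5 SD difference between blocks would produce a significant three-way term in roughly 14% to 21% of trials per outcome, under assumed splits from 85/15 to 67/33 and a change-score SD of 1, none of which the document supplies. A caveat would alter no estimate, test or p-value. This is an unstated limit that competent reporting supplies, plus one loose summary sentence that the next section clarifies.

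### Characteristics collected as potential confounders enter no outcome model: the app effect may be less precise than the data allow, and two- versus four-week contrasts compare non-randomised cohorts

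*Combined protocol and SAP*

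**What the plan says.** Under Outcomes, the plan says that characteristics linked in earlier literature to fruit and vegetable consumption and dietary knowledge "were also assessed as potential confounders". The paragraph on Demographic and Lifestyle Characteristics lists them: "gender, age, marital status, living status, number of years of education, smoking habits, alcoholic drinking habits, dietary supplement taking habits, and height and weight", the last two being used to calculate BMI.

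The Analysis paragraph gives them one use: "Demographic and lifestyle variables and all measures at baseline were first described and compared using t-tests, based on study duration and app / control". It then reports a finding, "Several important differences were found between those studied for two weeks and those studied for four weeks", and a response: duration is carried into every later analysis. Knowledge and intake outcomes go into a "2 (study duration) x 2 (app / control) x 2 (baseline / study end) mixed ANOVA". For the behavioural measure, "choice of fruit drink or non-fruit drink was analysed using Chi-squared tests". No listed characteristic appears in either analysis, and no reason is given.

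Under Intervention / Control, allocation to app or control was by lots at study entry. The test length followed the calendar: two weeks in the two November-to-March periods, four weeks in June to August 2016.

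**The concern.** Naming variables as potential confounders and then leaving them out of every outcome analysis is an internal mismatch. Two things are at stake.

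- **Precision of the app effect.** The target was 50 volunteers per arm with no power calculation, so unexplained variation matters. Baseline information is already collected and could reduce it.
- **Meaning of the duration terms.** The model yields a duration effect and an app x duration x time interaction. Duration was not randomised, and the plan itself reports that the cohorts differed. A reader of the results could take a duration finding as an effect of longer use when it may reflect different people or a different season.

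**Working it through.** The documents give no effect size, SD, correlation or R², so there is no planned figure to reproduce. Inputs from the plan are n = 100 (50 per arm), three test periods, two analysed time points, and "Significance was set at p<0.05" (two-sided assumed). Everything else is marked as assumed.

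**1. What the mixed ANOVA tests.** With two time points, the app x time term compares mean change between arms. A stable characteristic that shifts the outcome equally at baseline and study end cancels out of it.

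**2. Adjusting for the baseline outcome.** With equal SD (set to 1) at both times and correlation r:
- change-score variance = 2(1 − r)
- ANCOVA variance = 1 − r²
- ratio = (1 + r)/2

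The smallest effect detectable with 80% power is (1.96 + 0.842) x SD x √(2/50) = 0.560 x SD.

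| r (assumed) | Variance ratio | Detectable effect, change | Detectable effect, ANCOVA |
|---|---|---|---|
| 0.5 | 0.75 | 0.56 | 0.49 |
| 0.7 | 0.85 | 0.43 | 0.40 |
| 0.8 | 0.90 | 0.35 | 0.34 |

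**3. Adding three characteristics.** For p added covariates in a model that already has b parameters, the variance factor is about (1 − R²) x [1 + p/(n − b − p − 2)]. With intercept, arm, period (2 terms) and baseline value, b = 5. With p = 3 the penalty is 1 + 3/90 = 1.033.
- R² = 0.05, 0.10, 0.20 of the remaining variance (assumed): factors 0.98, 0.93, 0.83.
- Break-even: 1 − 1/1.033 = 0.032, about 3%.
- R² = 0: a loss of about 3%.

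Suppose the characteristics explain a share q of the outcome level equally at both times. Their share of what remains after baseline adjustment is q(1 − r)/[(1 − q)(1 + r)].
- q = 0.20, r = 0.5: 0.10/1.20 = 0.083, factor 0.917 x 1.033 = 0.95.
- q = 0.10, r = 0.8: 0.02/1.62 = 0.012, factor 0.988 x 1.033 = 1.02.

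So under these assumptions the characteristics give anything from about a 6% gain to a 2% loss.

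**4. Why the list must be short.** About ten terms for all the characteristics, with b = 6 parameters already in the model, give a penalty of 1 + 10/82 = 1.122 and a break-even R² of about 0.11.

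**5. Bias in the app effect.** This was simulated with 10,000 runs per setting. The assumptions were cohorts of 66 and 34, a covariate 0.8 SD higher in one cohort with slope 0.5 on change, and no true app effect.

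| Share given the app, by cohort | Model | Bias in app effect | Type I error |
|---|---|---|---|
| 50% / 50% | no duration | 0.00 | 4.6% |
| 50% / 50% | with duration | 0.00 | 5.0% |
| 40% / 70% | no duration | +0.10 | 7.5% |
| 40% / 70% | with duration | 0.00 | 4.6% |

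The duration factor protects the app comparison even when the arm split differs between cohorts.

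**6. Duration contrasts.** In the same simulation the duration effect on change was +0.40 (= 0.8 x 0.5) with no true duration effect. It fell to about 0 only when the covariate was added. For app x duration x time:
- If the covariate only shifts change, randomisation within period already leaves the interaction unbiased.
- If it modifies the app effect by 0.5 per SD (assumed), the bias is again 0.8 x 0.5 = 0.40. A main-effect covariate does not remove it; a covariate x app term would be needed.

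Season stays inseparable in either case, because each calendar period had one test length.

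**The case against.** A reader might infer that the reported cohort differences are uncontrolled and distort the app result. The documents do not support that. The plan answers those differences by adding duration to the ANOVA, and app or control was drawn by lot at entry, so the comparison is randomised within each period. The unadjusted app x time test is valid, and covariate adjustment for precision is optional, especially in a pilot with no power target.

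A reader might also take the factors 0.93 and 0.83 to mean 8% to 21% more volunteers at no cost (1/0.93 and 1/0.83). Those factors assume that the characteristics explain 10% to 20% of the residual variance. The plan says only that they are associated with consumption and knowledge, not with change, so the gain may be small or nil.

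Nor would adding the characteristics rescue the duration contrasts. Main-effect covariates do not remove effect modification, and no covariate separates season from duration.

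The choice of age, gender and education is a judgement, since the plan does not rank its characteristics. Finally, recruitment ended in March 2017, the document is dated April 2019, and it reports analyses in the past tense. A new covariate list could not be shown to be pre-specified.

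All of this stands. What it leaves is the unexplained mismatch between the stated role of the characteristics and their use, the more dependable gain from baseline adjustment, and the non-randomised status of the duration contrasts.

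**Conclusion.** The point holds as one of precision and interpretation, not of bias in the app effect. The characteristics labelled potential confounders enter no outcome model, and the plan does not say why.

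The more dependable gain comes from adjusting for the baseline outcome: variance about 0.75 to 0.90 of the change analysis, if r is 0.5 to 0.8 and the SD is similar at both times. Age, gender and education improve on that only above about 3% of the remaining variance, and the documents cannot show whether they reach it.

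The duration main effect and app x duration x time compare calendar cohorts that the plan itself found to differ. They cannot be read as effects of a longer test. The confounding figure of 0.40 illustrates the mechanism under assumed values; it does not estimate this trial's bias.

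**What to change.** Analyse each end-of-study knowledge and intake outcome by ANCOVA with:

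- app or control;
- test period (three levels), which replaces duration because period fully determines it;
- the baseline value of that outcome;
- a short fixed list of covariates, for example age, gender and years of education, chosen without reference to outcome results or baseline tests.

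Report the unadjusted result beside it, and label the adjusted analysis post hoc if outcomes have been seen. Describe any two- versus four-week contrast as non-randomised and exploratory. State how the remaining potential confounders were used, or that they were used only for description.

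The cost is a few degrees of freedom and some wording; the data are already collected. If the three characteristics explain nothing, they lose about 3% in precision. Even then the whole package remains a net gain at the assumed correlations. Four added terms (baseline value plus three) to a model with four parameters (intercept, arm, two for period) give a penalty of 1 + 4/90 = 1.044. The variance relative to the change analysis is then 0.75 x 1.044 = 0.78 to 0.90 x 1.044 = 0.94.

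### The app x time test in the mixed ANOVA is valid but fixes the baseline slope at 1; using the baseline score as a covariate is almost always at least as precise, with a material gain at moderate baseline-to-end correlation and, if the SDs are similar, a small one at 0.8 or more

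*Combined protocol and SAP*

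**What the plan says.** The Analysis section puts all questionnaire knowledge and intake outcomes through a "2 (study duration) x 2 (app / control) x 2 (baseline / study end) mixed ANOVA". Outcomes were collected "at baseline, at a mid point, and at study end" (Outcomes), but only the first and last of these enter the model. Duration is a factor because "Several important differences were found between those studied for two weeks and those studied for four weeks". For the intention-to-treat analysis, "missing data were completed using Last Observation Carried Forward". On reporting, the section says "All data are reported as means and standard deviations. Significance was set at p<0.05".

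On size, the Volunteers section aims for 50 per arm and explains that "No earlier research was available to allow power calculations". Under Intervention / Control, "recruitment stopped once 50 individuals had been randomized to test the app", so the number of controls was not fixed. Duration followed the calendar: two weeks for November 2015 to March 2016 and again "from Nov. 2016 - March 2017, and for four weeks from June 2016 - August 2016".

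The document does not name the ANOVA term that tests the app. It gives no model with the baseline score as a covariate, no correlation between baseline and study end, and no SDs.

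**The concern.** The only term in this ANOVA that carries the randomized comparison of change is app x time. With two time points it subtracts the whole of each volunteer's baseline from the end score, which is the best adjustment only if the true slope of end on baseline is 1. When the slope is lower, the subtraction adds baseline noise to the comparison.

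It also over-corrects chance imbalance. With 50 per arm the baseline difference between arms has a standard error of sqrt(2/50) = 0.2 SD. At rho 0.5 with equal SDs, an imbalance of that size moves the change-score estimate by (1 - 0.5) x 0.2 = 0.1 SD in the opposite direction.

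Because the sample size was not derived from power and results are judged at p<0.05, whether a real effect on any one outcome shows up depends on the standard error of that outcome's test. The trial is a pilot, so the precision of its estimates also matters for planning a later study.

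**Working it through.** There is no power-based figure in the document to reproduce; the planned 100 is simply 50 + 50.

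**Equivalence.** On one simulated data set, the app x time F from the mixed ANOVA and the app F from regressing change on app, duration and app x duration were both 0.7351. The stated test is a change-score test.

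**Residual variance.** Take baseline SD 1 and k = SD_end/SD_baseline.
- Change score: 1 + k^2 - 2 rho k
- Baseline as covariate: k^2 (1 - rho^2)
- Difference: (1 - rho k)^2, which is never negative

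With k = 1 these are 2(1 - rho) and 1 - rho^2, and their ratio is (1 + rho)/2. Estimating the slope costs a factor of about 1 + 1/94. The ordering therefore turns where (1 + rho)/2 x 95/94 = 1, that is, at rho = 0.979. Simulated ratios were 1.00 at rho 0.98 and 1.01 at 0.99.

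**Standard error.** With the two durations weighted equally, SE^2 = variance x (1/4) x (sum of 1/n over the four cells). For 33 two-week and 17 four-week volunteers per arm, the multiplier is (1/4)(2/33 + 2/17) = 0.0446. For 25/25 it is 0.0400. At rho 0.5 and 33/17:
- Change score: half-width 1.985 x sqrt(1.00 x 0.0446) = 0.42 SD
- Covariate model: half-width 1.985 x sqrt(0.75 x 0.0446) = 0.36 SD

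**Simulation.** All of the following are assumptions: 50 per arm split 33/17 (two November-March windows against one June-August window), equal SDs, a true effect of 0.5 SD and a 0.3 SD shift of the four-week group at both times. There were 40,000 trials per setting, and both models kept app x duration. Carried-forward volunteers were chosen at random at the same rate in each arm. In the table each arrow runs from the stated ANOVA to the covariate model; half-widths and powers are simulated.

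| rho | Ratio, closed form | Ratio, simulated | 95% CI half-width (SD) | Power, none carried | Ratio, 20% carried | Power, 20% carried |
|---|---|---|---|---|---|---|
| 0.3 | 0.65 | 0.66 | 0.49 → 0.40 | 0.51 → 0.69 | 0.73 | 0.42 → 0.54 |
| 0.5 | 0.75 | 0.76 | 0.42 → 0.36 | 0.65 → 0.77 | 0.81 | 0.55 → 0.63 |
| 0.7 | 0.85 | 0.86 | 0.32 → 0.30 | 0.86 → 0.91 | 0.90 | 0.76 → 0.80 |
| 0.8 | 0.90 | 0.91 | 0.26 → 0.25 | 0.96 → 0.97 | 0.94 | 0.90 → 0.92 |
| 0.9 | 0.95 | 0.96 | 0.187 → 0.183 | both above 0.99 | 0.97 | both above 0.99 |

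Type I error at 0% and 20% carried was 4.9-5.3% for app x time and 4.8-5.3% for the covariate model.

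**Last observation carried forward.** If a fraction m keeps its baseline value, the correlation becomes rho(1 - m) + m. At rho 0.5 and m = 0.2 that is 0.60, giving a closed-form ratio of 0.80. The effect is diluted to 0.8 x 0.5 = 0.40 SD in both models. At rho 0.5 the simulated ratio is 0.79 with 10% carried and 0.84 with 30%. It is also 0.79 if half of the 20% carry a mid-point value reflecting half the effect.

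**Other sensitivities at rho 0.5, none carried unless stated.**
- Even 25/25 split: ratios unchanged; power 0.69 → 0.81, or 0.59 → 0.68 with 20% carried.
- 40 controls: power 0.60 → 0.72. 60 controls: power 0.69 → 0.80.
- Unequal SDs: ratio 0.57 at k = 0.8 and 0.89 at k = 1.25.

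Unequal SDs matter at high rho too. At rho 0.8 and k = 0.8 the formula gives 0.64 x 0.36 / (1 + 0.64 - 1.28) = 0.64. At rho 0.8 and k = 1.25, where rho x k = 1, there is no gain (simulated 1.01).

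**Why app x duration stays.** Dropping it would cut the variance by about 10% at 33/17 (0.0400/0.0446 = 0.90), but it would change the target. With assumed effects of 0.3 SD at two weeks and 0.7 SD at four, both like-for-like models average 0.50. The model without the interaction averages 0.66 x 0.3 + 0.34 x 0.7 = 0.44.

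**The case against.** The strongest reply is that nothing is wrong: the stated test is valid, and preferring a covariate is a choice about efficiency. Certainty about the ordering says nothing about the size of the gain, and features of the trial point to the small end. The same questionnaire is repeated after two or four weeks, the structured intake question asks about typical days, and carrying baseline forward raises the correlation further. At rho 0.8 with equal SDs the half-width moves only from 0.26 to 0.25. The larger gains, at rho 0.3, have no support in the document. The trial is a completed pilot meant to gather feedback and look for potential impacts, and a supplementary re-analysis does not deliver the tabulated power, because the ANOVA remains the stated test. It also adds one more test per outcome, with no primary outcome or multiplicity control described.

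Much of this stands. The gain may be small, the power figures describe how sensitive each model would be as the deciding test, and what the re-analysis offers now is an interval that may be narrower. That app x time is the test of the app, and that the factorial weighting is equal, are also readings of the document. The 33/17 split is arbitrary. Counting calendar months (10 against 3) gives about 38/12 and a multiplier of (1/4)(2/38 + 2/12) = 0.055, which widens the intervals of both models and leaves the ratios alone.

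It does not remove the point. The ordering does not depend on the unknown rho, apart from a loss of about 1% of variance when the true slope is close to 1. High rho implies a small gain only if the SDs are similar at the two times. The baseline scores are already held.

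**Conclusion.** The concern holds as a missed gain in precision; the stated test is not in error. App x time is a valid change-score test under randomization. The covariate model with the same terms estimates the same effect and is essentially always at least as precise. With equal SDs the variance falls by 25% at rho 0.5, 10% at 0.8 and 5% at 0.9. Put the other way, the stated analysis needs 33% (1/0.75), 11% (1/0.90) or 5% (1/0.95) more volunteers for equal precision.

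Confidence is high in the ordering but not in the size. Rho, the SDs, the effect, the duration split and the fraction carried forward are all assumptions. The validity check covers carry-forward that is random and equally frequent in both arms, and so does not cover informative dropout. The re-analysis is worth doing, but the stated results do not depend on it for their validity.

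**What to change.** For each questionnaire knowledge and intake outcome, regress the study-end score on app/control, study duration, app x duration and that outcome's own baseline score. Effect-code the factors so that the app effect weights the two durations as the factorial ANOVA does. Entering baseline in the mixed ANOVA as a between-subject covariate without a baseline x time term would leave the app x time test unchanged, so use the regression or include that term.

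Report the adjusted app-control difference with a 95% CI beside the stated ANOVA and label it as a re-analysis that was not prespecified. The document is dated 15.04.19, recruitment ended in March 2017 and the Analysis section already describes results. Keep the ANOVA as the stated analysis. Where the two differ, say so, and do not choose between them by p-value. Also report, per outcome, rho, the baseline and study-end SDs, and the number of values carried forward.

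The cost is one regression per outcome and one residual degree of freedom (95 against 96 at 100 volunteers); no new data are needed. The change does not apply to the chi-squared analysis of drink choice and does not cure the dilution from carrying values forward, which affects both models.
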